## 4) Study Design

We propose a pilot clustered interventional trial with two arms. Clinics in the intervention arm receive Autism ALERT plus an ASD screening intervention (START Autism), and clinics in the comparison intervention (control) arm receive only START Autism (no Autism ALERT). As this is a pilot trial, primary outcomes of interest are feasibility and acceptability. We will additionally assess mechanism of outcome, preliminary efficacy, and protocol fidelity. Feasibility and acceptability will be assessed in intervention clinics. Mechanism of action and preliminary efficacy will be assessed by comparing intervention to control clinics. Fidelity is assessed in both arms. We will pilot test Autism ALERT in 6 safety-net primary care clinics in Oregon: 3 clinics will serve as intervention clinics, receiving both Autism ALERT and START Autism, and 3 clinics will serve as controls receiving START Autism only. Study arm will be assigned via coin-flip randomization of clinics, stratified for size and urbanicity, by a statistician who is not otherwise part of the study team.

In 2023 we received new funding from CareOregon to expand the project. As a result, this pilot study will be expanded to all of Portland-metro area. It will no longer include a control arm. Participants will be recruited off of Autism clinic waiting lists in the PDX metro area, and will be enrolled into the study to receive family navigation services from our partners at Help Me Grow.

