## **8) Data Analysis**

Process data from CCMT and Navigator Fidelity Checklist will be used to calculate contact attempts, time to first contact, total time spent per family, and counts of specific navigator activities. Families who complete all calls will be compared to those who broke off contact, and specific points of participant drop-off will be calculated. We will assess whether specific intervention activities varied by family demographic characteristic and clinic site, to assess variability in acceptability, using bivariate analyses. Family survey data will also be used to assess feasibility and acceptability. Initial analyses will focus on families who participated in ALERT, assessing experience of care and improvement suggestions. Next, post-intervention family experience will be compared in intervention vs. control clinics using bivariate analyses with an intention-to-treat approach. We will also examine variation in experience outcomes overall, and by study arm, by demographic characteristics, in order to assess whether the intervention was appropriate for diverse families, and to target improvements. Parent responses to open-ended items will be assessed via conventional content analysis. Using the parent interviews, we will also qualitatively assess families' feelings towards the evaluation process, and for the intervention arm we will also be looking at experiences with family navigators.

PCP process data will be used in a similar fashion. PCP/Navigator interactions will be descriptively characterized, using the PCP-Navigator Con-tact log and use of the PCP Website. PCP survey data will be used to characterize PCPs' post-intervention experiences. PCPs' overall experiences will be compared in both arms using bivariate testing, and open-ended questions will be coded.

We will refine our mechanism hypotheses and measurement by examining change in family-and provider-reported outcomes (e.g., stress, empowerment) pre-and post-intervention, in both study arms, primarily using descriptive and bivariate tests. Exploratory analyses will assess whether mechanism outcomes differ by family race/ethnicity, English proficiency, or insurance type, both overall and by study arm, using bivariate or limited multivariable regression analyses. This will allow us to gather valuable descriptive data on variation in engagement of target mechanisms, which might allow for individualized messaging in future research.

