We will compare efficacy outcomes in the Autism ALERT group to the baseline and control groups, using bivariate analyses and Kaplan-Meier curves for time to treatment variables. Estimated effect sizes for the subsequent R01 will be measured using Cohen's d. To test engagement of target mechanisms, we will assess whether efficacy outcomes differed by mechanistic outcome (e.g., whether parental stress was associated with time to treatment), using bivariate or limited multivariable models. We will also assess whether outcomes differ according to family demographic characteristics, both overall and by study arm, to test variability in intervention effects. Secondary and exploratory efficacy outcomes from ecWeb and Medicaid claims will be analyzed in the same framework.

Fidelity outcomes include both structural measures (e.g., receipt of program components) and procedural measures (e.g., quality of delivery of these components). We will use descriptive

statistics to assess delivery of the START Autism ± Autism ALERT training curriculum components. We will also use descriptive statistics to calculate navigator fidelity to the protocol, using the Navigator Fidelity Checklists. Checklists will also be cross-checked with recorded calls to assure accurate documentation. We will use descriptive statistics to characterize PCP use of the Autism ALERT website. To understand how Autism ALERT and START Autism altered PCP screening and referral behaviors, we will assess rate of ASD screening and EI/ECSE referral in both study arms in the baseline condition, and 3-and 6-months after initiation of START Autism ±Autism ALERT. As an exploratory analysis, we will assess whether racial/ethnic or language differences in PCP screening are present, and whether they vary by study arm or by PCP/clinic characteristics.

Our goals in this pilot study are to assess the feasibility and acceptability of the intervention and analysis, develop hypotheses regarding mechanism of action, and to provide context for defining meaningful differences and otherwise inform R01 power calculations. We intentionally have not powered to detect statistically significant differences. However, estimates will provide preliminary evidence of intervention effects, generate effect size estimates, and will help refine analytic strategy, efficacy hypotheses, and sample size estimates for a larger study.

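### Section 8 tests variation in the ALERT effect by comparing outcomes across demographic groups, which shows prognosis; the arm-by-characteristic contrast should be named, and the mechanism and effect-size estimates stated as ALERT versus control

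*Protocol*

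**What the plan says.** Protocol section 4 sets the comparison: "Mechanism of action and preliminary efficacy will be assessed by comparing intervention to control clinics". Clinics are randomised, stratified for size and urbanicity. Section 5 a) plans 25 intervention, 25 control and 20 baseline-condition dyads.

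Section 8 then describes the analyses:

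- **Effect variation, family outcomes:** "We will also assess whether outcomes differ according to family demographic characteristics, both overall and by study arm, to test variability in intervention effects".
- **PCP screening, by contrast:** the exploratory question is "whether racial/ethnic or language differences in PCP screening are present, and whether they vary by study arm or by PCP/clinic characteristics".
- **Mechanism scales:** the plan is "examining change in family-and provider-reported outcomes (e.g., stress, empowerment) pre-and post-intervention, in both study arms, primarily using descriptive and bivariate tests". Section 6 provides family surveys at enrolment and six months later, and provider surveys at enrolment and at the end of the intervention period.
- **Experience:** "post-intervention family experience will be compared in intervention vs. control clinics using bivariate analyses with an intention-to-treat approach". PCP experience is also compared between arms.
- **Efficacy and effect size:** "We will compare efficacy outcomes in the Autism ALERT group to the baseline and control groups". The next sentence reads "Estimated effect sizes for the subsequent R01 will be measured using" Cohen's d.

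The number of clinics is not consistent. Section 4 says "We will pilot test Autism ALERT in 6 safety-net primary care clinics in Oregon", while section 5 a) seeks seven practices and section 5 d) describes payment at six sites plus one more.

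**The concern.** The effect-variation sentence gives a purpose and a method that do not match. If a characteristic such as insurance type is related to outcome equally in both arms, outcomes will differ by that characteristic overall and within each arm, although the ALERT effect is the same for everyone. A prognostic factor could then be reported as a modifier of the effect.

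For the mechanism scales, the plan names change in both arms but does not write down the ALERT-minus-control estimate that section 4 points to. Bivariate tests of change also leave unused some of the precision in the enrolment scores.

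For Cohen's d, the preceding sentence has two comparators, and only the control group belongs to the randomised comparison.

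Section 8 says these estimates will inform the R01 power calculations, so which contrast they describe matters.

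**Working it through.** The protocol states no power, SD, correlation or ICC, so there is no figure of its own to reproduce. The counts add up: 20 + 25 + 25 = 70. The figures below are in SD units of a continuous family outcome and assume that all 25 dyads per arm are analysed, with two-sided 5% tests and 95% intervals.

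**1. Effect variation**

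*Precision of the right contrast (clinics ignored).* The contrast is the ALERT-minus-control difference in one demographic group minus that in the other.

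- Even split: variance 2 × (1/12.5 + 1/12.5) = 0.32, half-width 1.96 × √0.32 = 1.11 SD.
- 30/70 split: variance 2 × (1/7.5 + 1/17.5) = 0.381, half-width 1.96 × √0.381 = 1.21 SD.
- For comparison, the simple arm difference: variance 2/25 = 0.08, half-width 1.96 × √0.08 = 0.55 SD.

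*What would happen if each arm were tested separately.* Assume a 12/13 split in each arm and the same subgroup difference in both arms, so that the true effect does not vary. With p the within-arm power of the two-sample t-test, the chance that exactly one arm is significant is 2p(1−p).

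| Equal subgroup difference | p | Exactly one arm significant |
|---|---|---|
| 0.5 SD | 0.224 | 2 × 0.224 × 0.776 = 0.35 |
| 0.8 SD | 0.482 | 2 × 0.482 × 0.518 = 0.50 |

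A direct test of the contrast is significant in 5% of such trials, as it should be.

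**2. Mechanism scales**

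With enrolment-to-follow-up correlation r, the variance relative to a follow-up-only comparison is 2(1−r) for the change score and 1−r² after adjustment for the enrolment score. The ratio is (1−r²)/[2(1−r)] = (1+r)/2.

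- r = 0.5: ratio 0.75, √0.75 = 0.87, interval about 13% narrower.
- r = 0.7: ratio 0.85, √0.85 = 0.92, interval about 8% narrower.

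Now allow for clinic, with six equal clinics (25/3 dyads each, 4 df, t = 2.776) and an assumed ICC of 0.01 to 0.05. The design effect 1 + (25/3 − 1) × ICC is 1.073 to 1.367. The follow-up-only half-width is 2.776 × √(0.08 × 1.073) = 0.81 to 2.776 × √(0.08 × 1.367) = 0.92 SD. Multiplying by √[2(1−r)] or √(1−r²), and assuming the same reduction within and between clinics:

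| r | Change score | Adjusted for enrolment score |
|---|---|---|
| 0.5 | 0.81 to 0.92 SD | 0.70 to 0.80 SD |
| 0.7 | 0.63 to 0.71 SD | 0.58 to 0.66 SD |

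Seven clinics split 3/4 would give 5 df and slightly narrower intervals. Strata would take further degrees of freedom, but their number is not stated. With 15 providers per arm (section 5 a), provider scales have fewer subjects; the ratio (1+r)/2 is unchanged.

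**3. Cohen's d**

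No arithmetic applies. Section 4 ties preliminary efficacy to intervention versus control. Section 8 adds the baseline group as a second comparator and then names d without choosing between them.

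**The case against.** **The sentence may already mean the right thing.** Its stated purpose could be read as asking whether differences vary by arm. That is possible, but the PCP-screening sentence in the same section says so and this one does not.

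**Separate tests in each arm are never announced.** This stands. A reader might infer that the plan carries a 35% to 50% false-positive rate for effect variation. The documents do not support that: the figures hold only if each arm is tested alone and disagreement is read as variation. Nor would finding a difference in the pooled sample be an error in itself, since that detects a real prognostic association.

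**Section 4 already promises the arm comparison for mechanism.** This stands too. A reader might infer that section 8 contradicts section 4 or abandons the between-arm comparison. It does not: efficacy, family experience and PCP experience are compared between arms, and the mechanism wording does not exclude comparing the changes. A change-score comparison is also valid under randomisation and does use the enrolment score. Adjustment is a gain in efficiency, and model detail may sit in an analysis plan that is not shown.

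**Cohen's d has a context.** Agreed. Section 4 points to control, so only an explicit choice is lacking.

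**Little is at stake.** The primary outcomes are feasibility and acceptability, power is expressly disclaimed, and the subgroup contrast will be very imprecise. This limits the weight of the point. It does not make the current effect-variation wording answer its own question.

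**Conclusion.** The first part holds: the method as worded does not test the stated purpose, and the correct estimate is exploratory at a half-width of about 1.1 to 1.2 SD. The second part is an improvement and not the removal of a contradiction, worth about 8% to 13% in interval width at correlations of 0.5 to 0.7. The third is a minor clarification. The sizes rest on assumed subgroup splits, correlations and ICCs, equal clinic sizes and complete data. All of it concerns secondary or exploratory analyses of the unpowered pilot, and none concerns the expansion. The changes are optional but worthwhile.

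**What to change.** - **Effect variation:** replace the sentence with the arm-by-characteristic contrast for each family outcome, reported as an estimate with its interval and labelled exploratory. The section's own PCP-screening wording can be reused.
- **Mechanism scales:** state the estimate as the ALERT-minus-control difference at follow-up, adjusted for the enrolment score, with an interval that allows for the randomised clinics. Take the degrees of freedom from the actual number of clinics and strata, after reconciling six clinics in section 4 with seven in section 5 a).
- **Effect size:** say that Cohen's d for the R01 comes from ALERT versus control, and that ALERT versus the 20-dyad baseline group is descriptive.

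The cost is analysis wording only, since the surveys are already planned at both times. Allowing for clinic widens the intervals: at r = 0.5 with six clinics, 0.70 to 0.80 SD even after adjustment, against 0.55 SD for an unadjusted change-score arm difference that ignores clinic. The subgroup contrasts will also be visibly imprecise.

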## 3) Background

Children with ASD can be accurately identified as early as two years old. Children identified early and placed promptly into comprehensive treatment models [CTMs] such as applied behavioral analysis programs, show improvements in language, IQ and adaptive functioning. Still, average age of ASD diagnosis in the US is around 4 years old, and is older for low-income and racial/ethnic minority children. Low-income and minority children are also less likely to be diagnosed with ASD, and are more likely to have severe features (e.g. comorbid intellectual disability). Although access to evidence-based ASD therapy is rapidly expanding, most children with ASD are not treated with evidence-based interventions, and minority children use Early Intervention and CTM therapies at the lowest rates. Thus, there is a strong need for interventions that connect low-income and minority children with existing services that they are eligible for and could access. Primary-care based screening for ASD and other developmental delays is increasing. As a result, more children with suspected ASD are identified and referred from primary care. However, unlike other conditions for which early identification and treatment are critical (e.g., hearing impairment, congenital metabolic disorders), there exist no statewide or national systems to ensure that children identified with ASD risk are promptly evaluated and treated. While ASD services are theoretically available for most children in the US, they are often not accessed, leaving a critical gap between identification of suspected ASD in primary care and access to ASD diagnostic and treatment services, particularly for low-income and minority children. Research by our team suggests that this gap exceeds 2 ½ years on average. However, our prior research has also shown that when PCPs help families connect with ASD services, ASD diagnosis and treatment is timelier, and timely diagnosis is associated with increased use of evidence-based services. As a result, we propose a model statewide intervention to close the gap between identification of suspected ASD in safety-net (i.e., underserved setting) primary care clinics and use of diagnostic and treatment resources, for low-income and minority children.

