key document to associate their names with their study IDs, will be sent follow-up emails, and will also be given the option to complete the survey via mail or fax. Paper surveys will be stored securely at OHSU as outlined above and destroyed approximately 6 months after publication of study results. The patient portal survey will be anonymous and no study ID or PHI will be entered. In addition to the survey, chart review data will be collected which contains information about each provider's practice patterns. These data are collected once every 3 months, in both arms. These data include number of children screened for ASD and number of children referred to EI/ECSE for an ASD concern. Note that referrals to Early Intervention are a separate process that is standard of care, and is not related to enrollment in the study. Providers will be encouraged to adhere to standard of care in terms of screening children for autism and referring to Early Intervention; however this process can be accomplished by usual methods without enrolling children in the study if providers prefer. Number of children screened for ASD, and screening test results, will be collected by a practice administrator, using an existing form that we have used in prior research projects. The administrator will be considered engaged in research through an IAA. This form will be encrypted and sent to the study team electronically using OHSU's secure server. Finally, fidelity data (e.g., PCP-Navigator Contact Log) will contain information about interactions between the PCP and the navigator. This file will be kept encrypted and stored on OHSU Box, a secure cloud server.

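### Every pilot clinic receives START Autism, so before-after PCP screening and referral rates cannot show what START itself changed; the design supports only the added effect of Autism ALERT

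*Protocol*

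**What the plan says.** Section 8 (Data Analysis), in the paragraph on fidelity outcomes, states the purpose: "To understand how Autism ALERT and START Autism altered PCP screening and referral behaviors, we will assess rate of ASD screening and EI/ECSE referral". The measurements are to be taken "in both study arms in the baseline condition, and 3-and 6-months after initiation of START Autism ±Autism ALERT".

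Section 4 (Study Design) defines the arms. "Clinics in the intervention arm receive Autism ALERT plus an ASD screening intervention (START Autism"), while "clinics in the comparison intervention (control) arm receive only START Autism (no Autism ALERT"). The allocation is: "3 clinics will serve as intervention clinics, receiving both Autism ALERT and START Autism, and 3 clinics will serve as controls receiving START Autism only".

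Section 3 (Background) describes the secular trend. On screening: "Primary-care based screening for ASD and other developmental delays is increasing". On referral: "As a result, more children with suspected ASD are identified and referred from primary care".

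Section 6 (Procedures) says of the provider chart review: "These data are collected once every 3 months, in both arms". It does not say how many of these quarterly points come before START begins. Section 5f says the record review will not continue in the later expansion, so the point concerns the pilot only.

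**The concern.** The purpose sentence asks two causal questions of one data set: what ALERT altered and what START altered. The first has a randomised comparator. The second has none, because no clinic is followed over the same months without START, and the Protocol describes neither a staggered start nor an adjustment for an existing trend. The Background section supplies a rival explanation that runs in the same direction for both outcomes.

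What is at stake is the interpretation of a rise. If screening or referral goes up by the same amount in both arms, the stated purpose invites the reading that START did it. The data would look the same had START done nothing and practice been improving anyway.

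**Working it through.** The Protocol gives no screening rate, trend size, sample size or test for this outcome, so there is no planned figure to reproduce. The check is whether the design can identify a START effect.

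**1. Model for the cell means.** Let a = 1 for ALERT + START and a = 0 for START only, and let t be baseline or follow-up. Then

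m(a, t) = μ + γ·a + β·post + σ·post + δ·a·post

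Here β is background change (trend, season, being observed), σ is the START effect and δ is the added effect of ALERT. Both β and σ multiply the same indicator, since every clinic has START at follow-up and none at baseline.

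**2. What each contrast estimates.**
- Change in the control arm: β + σ
- Change in the intervention arm: β + σ + δ
- Difference between the two changes: δ

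No combination gives σ alone.

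**3. Rank of the design matrix.**
- Baseline and one follow-up, two arms: 5 parameters, rank 4. β and σ are not separable.
- Baseline, 3 and 6 months with a free period effect at each follow-up: 8 parameters, rank 6. Not separable at either time.
- Baseline, 3 and 6 months with a strictly linear trend and a constant START step: 5 parameters, rank 5. Within the control arm the step becomes [m(3) − m(0)] − [m(6) − m(3)], so START is separated only by assuming that all change from 3 to 6 months is background and that it ran at the same pace before. The Protocol states no such assumption.

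**4. Numerical example (assumed rates).** Take a baseline rate of 40% in both arms, a background rise of 5 points, and no effect of START or ALERT. Each arm goes from 40% to 45%. The before-after change is 45 − 40 = 5 points, all of it background. The between-arm difference in change is 5 − 5 = 0, which is the correct answer for ALERT.

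**5. How often such a rise would look significant (illustration only).** The Protocol plans no test here. The inputs below are assumptions, apart from a volume guided by section 5f, which cites more than 2000 visits over 6 months in a prior study of similar design, or about 2000/2 = 1000 per quarter. I split these evenly over six clinics (about 166 each), with a baseline rate of 40% or 60%, a between-clinic SD of 0.5 on the logit scale, a clinic-by-period SD of 0 or 0.15, no treatment effect, two-sided 5% tests and 20,000 replicates.

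| Shared rise | Pooled two-proportion test, 6 clinics | Paired t-test on 6 clinic changes | Between-arm t-test of changes, 3 v 3 |
|---|---|---|---|
| 0 points | 4–5% (SD 0); 14% (SD 0.15) | about 5% | about 5% |
| 2 points | 13–22% | 8–11% | about 5% |
| 5 points | 55–60% | 25–44% | about 5% |
| 10 points | 96–99% | 72–95% | about 5% |

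The 14% at zero rise shows that part of the pooled test's excess comes from ignoring clustering. The paired t-test is the cleaner guide, since it holds about 5% when nothing changes. Done separately within one arm of three clinics, a 5-point rise gives 33–39% for the pooled test and 10–16% for the paired t-test. The between-arm contrast is unaffected by the shared rise throughout.

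**The case against.** The strongest reply is that the sentence is a statement of purpose, not an analysis rule. It sits among fidelity measures, its neighbours speak of descriptive statistics, and it names no test, model or attribution. The pilot is deliberately not powered, and its primary outcomes are feasibility and acceptability. Rates are collected in both randomised arms, so the between-arm contrast is available, and its exact form could properly be left to a statistical analysis plan that is not shown here.

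Much of this stands. Not naming the ALERT contrast is no fault in itself. What remains is that the stated aim includes learning what START altered, and no analysis plan can supply a comparator without START. Lack of power is no answer either: the point estimate itself absorbs the trend.

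Three stronger readings are tempting, and the text does not support them.
- A reader might infer that the Protocol credits a background rise to START. It does not say so; it leaves the two inseparable. Section 3 also speaks of primary care in general, gives no size, and does not describe these clinics over 3 to 6 months.
- A reader might infer that the change will go forward to the larger study as proof that the training works. Section 8 does say in general that estimates will give preliminary evidence of intervention effects. But it ties the effect sizes for the later grant to efficacy outcomes comparing the ALERT group with baseline and control, and the hypotheses in section 2 concern ALERT.
- A reader might take the simulated percentages as error rates of the planned analysis. They belong to tests that are not planned, under an assumed rise.

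**Conclusion.** The point holds for the START half of the purpose sentence. With START in every pilot clinic, its effect on PCP screening and EI/ECSE referral cannot be separated from background trend, season or observation, whatever the size of the trend. The bias in any START reading equals the background change, which the Protocol leaves unquantified; only its direction is given. The conclusion rests on the arm definitions in section 4 and on there being no START-free clinic, staggered start or modelled pre-START series in the text. It does not rest on the simulation.

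The randomised contrast for ALERT survives. A trend common to both arms cancels; chance differences in trend between a few clinics do not, and belong in its interval. The clinic count is itself uncertain: section 4 gives 6, while section 5a seeks 7, so about three per arm is the fair description. This is a modest correction to a secondary fidelity measure; feasibility and acceptability are unaffected.

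**What to change.** Reword the sentence in section 8 along these lines: *The effect of adding Autism ALERT on PCP screening and EI/ECSE referral will be estimated as the difference between arms in the clinic-level change from baseline to 3 months and to 6 months, with a 95% confidence interval. Change within each arm after START Autism begins will be reported as descriptive change over time and not as an effect of START Autism, because every clinic receives START and none is followed concurrently without it.*

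This needs one added contrast on chart data already collected quarterly in both arms, with no new clinics or data collection. Two costs should be accepted openly. The pilot gives up its claim about START. The ALERT interval will be wide: with three clinics per arm, a comparison of clinic-level changes has 3 + 3 − 2 = 4 degrees of freedom, so the 95% multiplier is 2.78 rather than 1.96.
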